9.8.3. Secondary Efficacy Analyses

The curve representing the cumulative failure rate over time will be plotted using the Kaplan-Meier estimates for the fexinidazole and NECT groups.

The difference in the failure rates at 18 months will be estimated. The hazard ratio with respect to NECT will be estimated using a Cox model along with the 95% confidence interval.

No imputation of missing data will be performed. Data on patients lost to followup will be censured just after the last available assessment. The time course of the failure rate for fexinidazole and for NECT will be compared using a mixed-effect logistic regression model for repeated measures. Treatment, centre, time, baseline CSF WBC, age and sex will be used as candidate covariables. The linear predictor will include treatment-by-time and treatment-bycentre, as well as age and sex interactions. A backwards selection procedure will be used to identify significant terms, excepting those that involve the primary effect of centre and treatment. No imputation of missing data will be performed, except if outcome is missing at an intermediate visit and the outcome before and after the missing outcome were favourable.

The time course of the failure rate for melarsoprol and effornithine will be based on historical data (see Figure 5; p 107). No statistical tests will be performed for comparison with historical controls.

9.9. Safety Analyses

All patients who received at least one dose of study treatment will be included in the safety analyses.

The percentage of patients with SAEs and/or AEs leading to treatment discontinuation will be presented for each treatment group and by system-organ class, using appropriate MedDRA preferred terms, according to the NCI CTCAE, version 4.03.

The percentage of patients with at least one AE will be described. Patients in whom an AE with the same preferred term occurred several times will be counted only once. If a patient experienced several AEs described using the same preferred term, the AE with the maximum severity will be used in the analysis. In addition, each SAE will be presented in a narrative describing all aspects of the medical event with a causality assessment.

AEs not leading to treatment discontinuation will be presented for each treatment group using the same classification as presented above.

The incidence of SAEs and AEs, along with the respective 95% confidence intervals will be presented for each treatment group, by category and by frequency. In other cases, only descriptive statistics will be presented.

Laboratory safety parameters, i.e. haematology and biochemistry, will also be presented for each treatment group, indicating the percentage of patients, the size of the increase in the value in relation to the ULN and baseline value, and changes in blood levels over time. Shift tables will be presented. A listing of patients with laboratory abnormalities will be provided.

ECG abnormalities will be presented for each treatment group and for each timepoint within each treatment group.

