2.1.3. Secondary Objectives

- To compare the time course of the failure rate with fexinidazole and NECT from the EOT visit to 24 months, i.e. the end of the long-term follow-up period.
- To compare the safety of fexinidazole with that of NECT in the treatment of late-stage sleeping sickness due to *T. b. gambiense*.
- To assess plasma and CSF concentrations of fexinidazole and its metabolites in all patients who receive fexinidazole, and to investigate the correlation between the concentration and the efficacy and safety of fexinidazole in patients with late-stage sleeping sickness due to *T. b. gambiense*.
- To compare the pharmacodynamic impact of fexinidazole and of NECT on QT/QTcF interval, as measured on ECG.

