8.4. Patients Lost to Follow-up

If a patient does not attend a protocol-planned visit, all necessary measures must be taken to contact him/her. In all cases, all necessary measures must be taken to document the outcome of the patient's condition, if possible.

9. Data Analysis and Statistical Methods

A draft of the full Statistical Analysis Plan (SAP) will be prepared prior to conducting the first FA. It will provide a more detailed description of the statistical methods. The SAP will be reviewed and, if necessary, amended prior to final database lock.

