9.1. Sample Size Determination

The calculation of the sample size has been revised. The total size of the sample is now calculated to be 390 patients, instead of 510, with the same 2:1 allocation ratio, i.e. 260 patients in the fexinidazole group and 130 patients in the NECT group. If the expected success rates are 94% with NECT and 89% with fexinidazole³ then the power of the final analysis is 80% with an acceptability ("non-inferiority") margin of 13%. The calculations were made for a one-sided type-1 error of 0.025.

No provision will be made for patients lost to follow-up since the missing outcome will be imputed, except for patients in areas of armed conflict (see Section 8.3).

³ The observed response rate for NECT was as high as 0.97 in the per protocol population and 0.965 in the ITT population (43). However, the definition of success was not the same as in this protocol, and the success rate for NECT would have been 0.95 or 0.94 if the same definition had been used. If fexinidazole has the same true success rate as NECT, and is equal to 0.95 or 0.94, then the power of the study will be greater than 99%. However, NECT is a co-administration of two drugs and there is no reason to expect fexinidazole to be more effective than effornithine alone. Available data show that the success rate with effornithine depends on the project and ranges between 0.89 and 0.90. If the expectations are 0.90 for fexinidazole and 0.95 for NECT, the exact power of the final primary analysis is 91.6%.

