9.10. Analysis of Other Endpoints

PK Data

For patients in the fexinidazole group:

- Concentrations of fexinidazole, M1 and M2 in whole blood and in CSF will be measured, with PK parameters derived using a population PK model.
- Analysis of all PK samples will be centralised. A population PK model will be developed using Nonmem software. The model will be fitted on rich sampling data from phase-I studies and used for sparse sampling data from phase-II studies. The model will be used to estimate population PK parameters, including clearance (CL) and volume of distribution (Vd). All of the analyses and statistical methods, including data conventions, will be described in detail in a separate SAP, which will be finalised prior to database lock.
- Correlations between blood and CSF concentrations will be described on samples collected at the EOT visit. Correlations between blood and CSF concentrations, on the one hand, and the success rate/AE rate, on the other hand, will be described.

Information on the PK data from the study will provide confirmation of phase-I data on a larger sample size, will allow for analysis of individual failures or intolerance, and will help predict the dose for a future study in early-stage HAT.

ECG Data

- QT/QTcF interval (mean, range and categories) at the various timepoints.
- Prolongation of QT/QTcF interval in relation to baseline.

All of the analyses and statistical methods, including data conventions, will be described in detail in a separate SAP, which will be finalised prior to database lock.

An interim analysis, involving ECG data from 195 patients, will be performed.

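### Comparing safety with NECT is a secondary objective, but section 9.9 gives confidence intervals within single arms only and names no between-arm safety estimate

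*Protocol*

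**What the plan says.** Section 2.1.3 of the protocol lists as a secondary objective: "To compare the safety of fexinidazole with that of NECT in the treatment of late-stage sleeping sickness". The protocol summary carries the same objective.

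Section 9.9 gives the method. The analysis set is simple: "All patients who received at least one dose of study treatment will be included in the safety analyses". Percentages of patients with AEs, SAEs and AEs leading to discontinuation are shown by arm. The incidence of AEs and SAEs, "along with the respective 95% confidence intervals will be presented for each treatment group". The section then adds: "In other cases, only descriptive statistics will be presented". Laboratory and ECG abnormalities are also shown by arm. No between-arm quantity is mentioned.

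Two neighbouring sections are worded differently. Section 9.8.3, on secondary efficacy, names its contrast: "The difference in the failure rates at 18 months will be estimated", together with a hazard ratio and its 95% interval. Section 9.10 says of the PK and ECG methods that they "will be described in detail in a separate SAP, which will be finalised prior to database lock". Section 9.9 does neither. The only deferral that reaches it is the general one at the start of section 9, which says of the SAP: "It will provide a more detailed description of the statistical methods".

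**The concern.** An objective to compare two arms calls for an estimate of how they differ and how precisely that is known. Section 9.9 chooses which intervals will be produced, and it chooses one per arm. Two single-arm intervals do not give the interval of the difference. A reader left with them has to combine them, and the usual shortcut of checking whether they overlap is too strict.

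What is at stake is the safety side of the benefit-risk reading. Section 9.8.1 says that the efficacy effect size and its 95% interval will take precedence over the test result when benefit and risk are weighed. Efficacy therefore enters as a difference with an interval. Under section 9.9 as written, safety enters as two separate columns. The study rationale and section 1.5 call for less toxic treatment, so the safety contrast is part of what the trial should inform.

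**Working it through.** **Inputs.** Arm sizes are from section 9.1: "260 patients in the fexinidazole group and 130 patients in the NECT group". The protocol gives no expected AE or SAE incidence, so the incidences below are assumptions.

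**Arm sizes checked.** The plan states no safety figure to reproduce. Its efficacy sample size does reproduce with 94% and 89% success, margin 13%, one-sided 0.025, 80% power and 2:1 allocation:

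- n(NECT) = (1.96 + 0.84)² × (0.94×0.06 + 0.89×0.11/2) / (0.13 − 0.05)² ≈ 7.85 × 0.10535 / 0.0064 ≈ 129.2, rounded up to 130. This gives 130 + 260 = 390.
- Power at that size is 80.2% by the normal approximation, against 80% stated.

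This confirms only the arm sizes used below.

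**Precision of a risk difference at 260 and 130.** With equal incidence p in both arms, half-width = 1.96 × √[p(1−p)(1/260 + 1/130)], where √(1/260 + 1/130) = 0.1074.

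| Assumed incidence in both arms | √[p(1−p)] | Half-width |
|---|---|---|
| 5% | 0.218 | 4.6 points |
| 10% | 0.300 | 6.3 points |
| 20% | 0.400 | 8.4 points |
| 50% | 0.500 | 10.5 points |

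A Newcombe score interval is similar. For 26/260 against 13/130 it runs from −7.1 to +5.9 points, compared with ±6.3 from the formula.

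**What single-arm intervals can hide.** Take 52/260 (20%) on fexinidazole and 13/130 (10%) on NECT:

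- Separate exact 95% intervals: 15.3% to 25.4%, and 5.4% to 16.5%. They overlap.
- Difference: +10.0 points, Newcombe 95% interval +2.3 to +16.7. It excludes zero.

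More generally, at equal incidence, non-overlap of two 95% intervals needs a difference (SE₁ + SE₂)/√(SE₁² + SE₂²) times as large as the interval of the difference needs. At 2:1 this is (1 + √2)/√3 = 1.39. The protocol does not plan to judge by overlap. The factor only shows what a reader loses when given nothing else.

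**The case against.** The strongest reply is that this belongs in the SAP. Section 9 says that the SAP will describe the methods in more detail, and a risk-difference column is ordinary SAP or table-shell content. Side-by-side rates by randomised arm are also a customary safety comparison, and the point difference can be read from them. The sentence about descriptive statistics covers output other than AE and SAE incidence, and it does not forbid a descriptive difference.

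Most of this stands, and it keeps the point minor. It does not remove it. Section 9.9 is not silent on intervals: it specifies them and places them within arms. It also lacks both the named contrast of section 9.8.3 and the specific deferral of section 9.10.

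A reader might draw several stronger conclusions that the document does not support:

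- *That no safety difference will ever be estimated.* This cannot be shown without the SAP.
- *That the arms will be judged by overlapping intervals.* No section says so.
- *That 2:1 allocation was chosen for the safety comparison.* Section 1.10 gives the reason as more patients exposed to fexinidazole, an aim that a single-arm interval serves.
- *That the 13% margin is the price of a safer drug.* Section 9.8.1 bases the margin on the practical advantage of an oral drug and on a physician survey. The wish for less toxic treatment appears only as a general need.

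**Conclusion.** The point holds in a limited form. The protocol sets an objective to compare safety, and section 9.9 states a method that confines intervals to single arms and names no between-arm estimate. As stated, the method gives the two rates but not the uncertainty of their difference. No stated figure is wrong.

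The missing interval would be informative, with half-widths of about 4.6, 6.3 and 8.4 points at incidences of 5%, 10% and 20%. These rest on assumed incidences, equal in both arms, and on the full 260 and 130 patients being dosed. The importance is low: this is a cheap improvement and does not threaten the trial's conclusions.

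**What to change.** In section 9.9, add the risk difference (fexinidazole minus NECT) with a 95% score interval, for example Newcombe's, because some counts will be small. Apply it to the main safety endpoints of section 2.2.2:

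- any AE in the observation period;
- any AE of grade 3 or higher in the observation period;
- any treatment-related AE in the observation period;
- any SAE over the follow-up windows.

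No test and no alpha are needed. State that the intervals are unadjusted and descriptive.

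The SAE windows must be settled first. Besides the window to month 18, section 2.2.2 counts SAEs between months 18 and 24, while section 6.5 counts them from first intake to month 24. The new column should follow whichever the sponsor keeps.

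If the sponsor prefers no between-arm estimate, the alternative is to reword the objective in the summary and section 2.1.3 as a description of safety in each arm. The first option costs one extra column in existing tables and a few more intervals to read with caution; the second costs one sentence.

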9.10. Analysis of Other Endpoints

PK Data

For patients in the fexinidazole group:

- Concentrations of fexinidazole, M1 and M2 in whole blood and in CSF will be measured, with PK parameters derived using a population PK model.
- Analysis of all PK samples will be centralised. A population PK model will be developed using Nonmem software. The model will be fitted on rich sampling data from phase-I studies and used for sparse sampling data from phase-II studies. The model will be used to estimate population PK parameters, including clearance (CL) and volume of distribution (Vd). All of the analyses and statistical methods, including data conventions, will be described in detail in a separate SAP, which will be finalised prior to database lock.
- Correlations between blood and CSF concentrations will be described on samples collected at the EOT visit. Correlations between blood and CSF concentrations, on the one hand, and the success rate/AE rate, on the other hand, will be described.

Information on the PK data from the study will provide confirmation of phase-I data on a larger sample size, will allow for analysis of individual failures or intolerance, and will help predict the dose for a future study in early-stage HAT.

ECG Data

- QT/QTcF interval (mean, range and categories) at the various timepoints.
- Prolongation of QT/QTcF interval in relation to baseline.

All of the analyses and statistical methods, including data conventions, will be described in detail in a separate SAP, which will be finalised prior to database lock.

An interim analysis, involving ECG data from 195 patients, will be performed.

9.11. Interim Analyses

Two types of interim analyses will be performed:

- interim futility analyses, the aim of which is to discontinue the study if the efficacy of fexinidazole is markedly inferior to expectations, and
- an interim analysis of success, the aim of which is to accelerate the process for submission of the registration dossier if the efficacy of fexinidazole is superior to expectations. Unlike with usual interim analyses of success, this study will be continued to completion regardless of the result of the interim analysis in order to obtain a precise idea of the relapse rate and rate of intercurrent events in the long term.

Interim Futility Analyses

Futility analyses will be performed in order to inform decisions about possible study discontinuation, based on pre-determined stopping rules. The aim is to limit the number of patients exposed to the IP in the event that the latter should prove to have limited efficacy.

An independent statistician with no involvement in preparing the study, in the blind review of data or in the final statistical analyses will be responsible for performing the FAs. Based on the analyses, s/he will be able to recommend continuing the study or stopping it due to futility. The independent statistician will be the only person able to access the randomisation code at the time of the FAs.

No information concerning the magnitude of the treatment effect will be provided. The ISC/DSMB may use additional or more stringent rules to stop exposure to fexinidazole, particularly in the event of safety concerns. The ISC/DSMB may decide to disregard recommendations based on the FAs if death is not related to treatment failure, but to accident, crime, etc.

The FAs will be performed on raw data on the ITT population.

The FAs will be performed as soon as data are available at a given timepoint. However, since the size of the sample increases at each timepoint, additional analyses may be performed at the written request of the ISC/DSMB to improve the statistical power of the analyses (see Table 5 – Overview of Protocol-planned Futility Analyses, and Table 7 – Expected Enrolment Rate).

Information concerning statistical power, criteria and the rules for the FAs is presented in Table 5 – Overview of Protocol-planned Futility Analyses (p 107).

The quantitative thresholds for decisions provided in the table are correct if the actual sample size is equal to the planned sample size.

Futility Analysis 1: EOT responder rate (n = 30). Performed if fewer than 27 out of 30 patients are responders at the EOT visit.

The 1st FA will be performed under certain conditions, once the outcome at the EOT visit is known for 30 patients, i.e. 20 patients exposed to fexinidazole and 10 patients exposed to NECT.

The blind will be lifted for the first 30 patients, and the analysis will be performed if and only if the number of responders is less than 27 out of 30 patients, based on the assumption that no deviations from randomised treatment assignment occur.

The study will be stopped if the actual percentage of responders in the fexinidazole group is significantly lower than 95%, which corresponds to the historical rate for melarsoprol at the end of treatment (published responder rate, p = 95.2%; n = 6840).

The test will be significant if the number of responders in the fexinidazole group is \leq 16 out of 20 patients.

Futility Analysis 2: EOT responder rate (n = 105). Performed if fewer than 98 out of 105 patients are responders at the EOT visit.

The 2nd FA will be performed under certain conditions, once the outcome at the EOT visit is known for 105 patients, i.e. 70 patients in the fexinidazole group and 35 patients in the NECT group.

The blind will be lifted for the first 105 patients, and the analysis will be performed if and only if the number of responders is less than 98 out of 105 patients.

The study will be stopped if:

 Rule 1: the actual percentage of responders in the fexinidazole group is significantly lower than 95%, which corresponds to the historical rate for melarsoprol at the end of treatment (published responder rate, p = 95.2%; n = 6840),

AND the percentage of responders in the NECT group is compatible with 99%.

The first test will be significant if the number of responders in the fexinidazole group is ≤ 62 out of 70 patients. The second condition will be met if the number of responders in the NECT group is ≥ 33 out of 35 patients.

 OR Rule 2: the percentage of responders in the NECT group is not compatible with 99%, AND the difference in the percentage of responders between fexinidazole and NECT is significantly higher than 4%, which corresponds to the historical difference at the end of treatment between melarsoprol and eflornithine (δ = 4%) (see Table 5 – Overview of Protocol-planned Futility Analyses; p 107).

The test for comparison of the difference between the rates with a margin of 4% will be performed using a modified Blackwelder test, i.e. difference greater than the margin instead of smaller than the margin.

Futility Analysis 3: responder rate 3 months after the EOT (n = 105). Performed if fewer than 94 out of 105 patients are responders at 3 months.

The 3rd FA will be performed under certain conditions, once 105 patients have performed the 3-month visit.

The blind will be lifted for the first 105 patients, and the analysis will be performed if and only if the number of responders is less than 94 out of 105 patients at 3 months.

The study will be stopped if:

 Rule 1: the actual percentage of responders in the fexinidazole group is significantly lower than 91%, which corresponds to the historical rate for melarsoprol at 3 months (see Table 5 – Overview of Protocol-planned Futility Analyses; p 107);

AND the actual percentage of responders in the NECT group is compatible with 99%.

The first test will be significant if the number of responders in the fexinidazole group is \leq 59 out of 70 patients. The second condition will be met if the number of responders in the NECT group is \geq 33 out of 35 patients.

OR Rule 2: the percentage of responders in the NECT group is not compatible with 99%,
 AND the difference in the percentage of responders between fexinidazole and NECT is significantly higher than 7%, which corresponds to the rounded historical difference between melarsoprol and effornithine at 3 months (see Table 5 – Overview of Protocol-planned Futility Analyses; p

107).

Futility Analysis 4: responder rate 6 months after the EOT (n = 105). Performed if fewer than 84 out of 105 patients have a favourable outcome at 6 months.

The 4th FA will be performed under certain conditions, once 105 patients have performed the 6-month visit.

The blind will be lifted for the first 105 patients, and the analysis will be performed if and only if the number of responders at 6 months is less than 84 out of 105 patients.

The study will be stopped if:

• Rule 1: the actual percentage of responders in the fexinidazole group is significantly lower than 80%, which corresponds to the historical rate for melarsoprol at 6 months,

AND the percentage of responders in the NECT group is compatible with 95%.

The first test will be significant if the number of responders in the fexinidazole group is \leq 49 out of 70 patients. The second condition will be met if the number of responders in the NECT group is \geq 30 out of 35 patients.

 OR Rule 2: the actual percentage of responders in the NECT group is not compatible with 95%,
 AND the difference in the percentage of responders between favinidezels.

AND the difference in the percentage of responders between fexinidazole and NECT ($p_{NECT} - p_{fexi}$) is significantly higher than 12%.

The 95% rate of favourable outcomes for NECT is lower than the historical rate (42), and slightly higher than the historical rate with effornithine. The 12% threshold corresponds to the rounded difference between the rate for effornithine and the rate for melarsoprol (see Table 5 -Overview of Protocol-planned Futility Analyses; p 107).

Futility Analysis 5: Favourable outcome rate at 12 months after EOT (n = 105). Performed if fewer than 80 out of 105 patients have a favourable outcome at 12 months.

The 5th FA will be performed under certain conditions, once 105 patients have performed the 12-month visit.

The blind will be lifted for the first 105 patients, and the analysis will be performed if and only if the number of responders at 12 months is less than 80 out of 105 patients.

The study will be stopped if:

• Rule 1: the actual percentage of responders in the fexinidazole group is significantly lower than 75%, which corresponds to the historical rate for melarsoprol at 12 months,

AND the percentage of responders in the NECT group is compatible with 95%.

The first test will be significant if the number of responders in the fexinidazole group is \leq 44 out of 70 patients. The second condition will be met if the number of responders in the NECT group is \geq 30 out of 35 patients;

OR Rule 2: the percentage of responders in the NECT group is not compatible with 95%,
 AND the difference in the percentage of responders between fexinidazole and NECT (p_{NECT} – p_{fexi}) is significantly higher than 13%.

This threshold is slightly lower than the historical difference between effornithine and melarsoprol at 12 months, i.e. \approx 15%. It should be noted that, at this stage, the study will be stopped if the result is significantly worse than the margin of an unacceptable difference, whereas the final analysis will be positive if the result is significantly better than the margin of an unacceptable difference.

Interim Analysis for Success

An interim primary analysis for success will be performed on the first 195 randomised patients who have theoretically reached 12 months of follow-up, excluding patients for whom no post-treatment data are available because the patient is known to have fled the area strictly for reasons of armed conflict. The analysis will be identical to the final primary analysis with the exception of the threshold for significance (see Adjustment of Type-I Error for Multiplicity) and the assessment visit, which will be 12 months instead of 18 months.

A sensitivity analysis, including all randomised patients, will be performed and will consider all patients who fled for reasons of armed conflict as failures.

If the interim primary analysis for success should not prove to be significant, no further interim secondary or sensitivity analyses will be performed. If the analysis proves to be significant, all of the interim secondary and sensitivity analyses will be performed in accordance with the approach described for the final analyses, i.e. those initially planned. In addition, the success rate at 18 months will be compared, using a superiority test, to the historical success rate for melarsoprol at 18 months, i.e. 73.7%. No adjustment of the threshold for significance will be made in this analysis. The time course of the success rate, i.e. EOT, 6 months, 12 months and 18 months, will be studied using the Kaplan-Meier approach. The cumulative failure rate at each visit will be presented graphically including historical data for melarsoprol and effornithine.

Adjustment of Type-1 Error for Multiplicity

No adjustment will be made for the FAs, because the study cannot be prematurely discontinued for success based on an FA. In this case, Chen has shown that performing such analyses slightly reduces the final type-I error (9).

An adjustment of the type-I error will be made in view of the interim analysis for success. The Pocock approach will be used to determine the threshold of significance of the interim analysis as well as that of the final analysis. As a reminder, the final analysis will be performed on the planned number of patients.

10. Independent Steering Committee/Data Safety Monitoring Board

An Independent Steering Committee (ISC or DSMB) composed of at least 3 members independent of the Investigators and the Sponsor, will be set up prior to study initiation. The ISC will monitor the study in order to minimise any risk of harm to the patients included in the study. At predetermined intervals, the ISC will analyse safety data and all information related to SAEs or AEs leading to treatment discontinuation, and will put forward recommendations regarding the study if the benefit-to-risk balance for patients seems to be in jeopardy. The data and the intervals for review will be decided before, or soon after study initiation and documented in the ISC Charter.

The results of FAs will be presented to the ISC, who will decide whether or not the study can continue and whether the enrolment period should be extended.

The organisation of the ISC will be described in the ISC Charter, which will be prepared and approved prior to the first planned FA.

Additional *ad hoc* members may be invited to join the ISC if any safety concerns emerge, in order to give additional support to the competencies already present.

11. Quality Assurance and Quality Control Procedures

The Investigator must maintain appropriate accurate records to ensure that all aspects of conducting the study are fully documented, and that study data can be verified at the end of the study. These documents include the Investigator Site File, the patients' clinical source documents, screening/enrolment logs and other study-specific forms.

